## **Glossary of Definitions and Terms**

High Flow Nasal Cannula (HFNC): Nasal cannula system that delivers flow rates of respiratory gas meeting or exceeding a patient's normal spontaneous inspiratory flow demand. HFNC systems must maintain adequate heating and humidification of the delivered gas to protect the airway tissues from dryness.

High Velocity Nasal Insufflation (HVNI): a system consisting of heated and humidified gas mixtures of varying FiO2 delivered to a patient using a small-bore nasal cannula, at generally high flow rates imparted with increased velocity as compared to other standard large-bore cannulae. The flow rates of respiratory gas generally exceed a patient's normal spontaneous inspiratory flow demand. HVNI systems must maintain adequate heating and humidification of the delivered gas to protect the nasal tissues from dryness and provide patient comfort.

Non-Invasive Positive Pressure Ventilation (NIPPV): Breathing assist where a mask is strapped tightly to a patient's face and bi-level positive airway pressure is administered at an established frequency to support patient ventilation.

Intubation: The placement of an endotracheal tube to facilitate respiratory support and provide airway protection.

Respiratory Failure: The inability to maintain sufficient arterial blood oxygen saturation and/or retention of carbon dioxide levels during unassisted spontaneous breathing.

Pulmonary Rehabilitation: Exercise regimen for patients with compromised cardio-pulmonary function designed to improve pulmonary parameters.

Pulse Oximetry Reading (SpO2): Indirect measure of a patient's arterial blood oxygen saturation using pulse oximetry technology that utilizes oxygen/hemoglobin concentrations.

Resting  $SpO_2$ :  $SpO_2$  value the patient demonstrated at rest, while sitting upright and connected to the pulse oximetry monitor prior to the start of the study session. This value will be patient specific and reflect oxygen saturation.

Desaturation  $SpO_2$ : The  $SpO_2$  value considered to be the point of desaturation where the value drops below a specified threshold. This value is based on the desaturation requirement for reimbursement of oxygen therapy.

Ventilatory Work Effort / Work of Breathing (WOB): The physical, physiologic muscular demands of breathing manifested through signs and symptoms of increased physical exertion, manifested through pulmonary changes leading to the use of accessory muscles for inspiration or exhalation.

Fraction of inspired oxygen (FiO2; %): The percent of the delivered respiratory gas mixture that is oxygen, expressed as a fraction.

Ventilatory Rate (Respiratory Rate; RR, BPM): The number of breaths a subject takes per minute (breaths·min).

Blood Pressure (BP): as measured by systolic and diastolic pressures of the blood contained in the circulatory system, measured for this study in mmHg.

Heart Rate (HR): The number of heart beats per minute (beats·min).

Modified Borg Scale (Borg): Dyspnea is an important measure of patient respiratory distress & pulmonary functional status. The rate of perceived dyspnea (RPD) is determined by patients and clinicians to using specific descriptors, on a scale of 0 (no dyspnea) to 10 (unbearable dyspnea). The modified Borg scale is additionally used for rating the subjective perceived exertion (RPE) during exercise, while at the same workload.

Standard of Care (SOC): Site standard practices for the medical care of patients presenting with specific symptoms.

Case Report Form (CRF): The form used to record pertinent patient data to address the study aim. CRFs do not contain patient names or medical record numbers; rather they will be coded with a patient number and the site principal investigator at each center will maintain the key. The CRFs are the property of Vapotherm.

Transcutaneous  $CO_2$  (TcPCO2): This non-invasive method of measuring circulating  $CO_2$  transdermally, indicating trends for arterial carbon dioxide levels using a locally heated electrochemical sensor applied to the skin, can be used to assess a patient's adequate ventilation and oxygenation.

## I. Background and Significance

Hypoxemia and dyspnea are hallmark characteristics of patients with chronic pulmonary disease and can be attributed to acute respiratory failure.  Oxygen therapy is generally a first stage in addressing dyspnea and hypoxia. Often times this therapy is delivered via various devices that provide pressure (mechanical ventilation [MV], non-invasive positive pressure ventilation [NIPPV]) and flow-based (high-velocity nasal insufflation [HVNI] and high flow nasal cannula [HFNC]) modalities to support oxygenation and ventilation, and in many cases, NIPPV & HVNI have been demonstrated to provide comparable support.  The key difference in these modalities can best be described by the alveolar ventilation equation: alveolar ventilation = (Inspired Volume – Dead Space) X Respiratory Rate. Inspired volume is achieved by adding pressure (NIPPV) and Dead Space is eliminated via HVNI; Two separate mechanism of actions that influence alveolar ventilation. HVNI is a therapeutic alternative to NIPPV.

Vapotherm HVNI therapy, a refined form of HFNC, is premised on the technical ability to create ideally conditioned medical grade vapor, which is delivered nasally with an intent to support spontaneous ventilation as opposed to simple oxygen therapy.  Vapotherm technology is unique in its ability to provide this conditioned gas through a small-prong nasal cannula resulting in a high velocity without the well-known adverse effects related to drying and cooling of the nasal mucosa.  The high velocity nasal flow facilitates a well described mechanism of improving ventilatory efficiency by way of eliminating carbon dioxide traditionally stacked in anatomical dead space of the upper airway. 

Upper airway purge is important to alveolar gas exchange as the gas that is drawn to the respiratory regions of the lungs comes from the dead space or anatomical reservoir created by the flush, in the same way that oxygen conservation masks (re-breathers) can incorporate reservoir bags to reduce the bulk flow requirements from the oxygen source to achieve the same oxygenation effect.  Based on mathematical modeling, physiologic studies and clinical observations, a flow rate of 4 to 8 L·min through Vapotherm's neonatal cannulae, or 25 to 40 L·min through Vapotherm's adult cannulae, would purge the anatomical reservoir of the upper airway in the window of time between breaths. 

Vapotherm's humidification system is specifically designed to tolerate a high back pressure in the humidification cartridge that is generated by passing these flow rates through small bore cannulae that result in the appropriate flow velocities (turbulent energy).  Since 2000, Vapotherm HVNI has been used extensively and has been well studied and the clinical impact of this ventilation effect using Vapotherm's conventional cannula line is well described  A multi-center recent randomized clinical trial also demonstrated the noninferiority of HVNI to NIPPV in the treatment of undifferentiated respiratory distress for patients presenting to the Emergency Department.  As Vapotherm leads the innovation of new cannulae for the purpose of HVNI, we seek to evaluate the ability of these cannulae to impact ventilatory work effort on dyspneic patients. The goals of the current study are to: (1) evaluate if next generation dual prong (Prosoft) cannulae provide comparable dyspneic relief among hypercapnic adults with accompanying dyspnea compared to current legacy (control) cannula design, and (2) assess if next generation Solo (Unicorn) cannulas at lower flows provide comparable dyspneic relief among hypercapnic adults with accompanying dyspnea compared to current legacy to Dual-prong cannula (Prosoft) design.

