## Phase 1 - Conventional Legacy cannula design (Control)

This test session is represented by Phase 1 in Figure 1, where the patient is placed on HVNI therapy with an appropriately fitted conventional legacy cannula design. Phase 1 will follow four distinct segments: (1) baseline characterization, (2) therapy acclimatization, (3) therapeutic characterization, (4) patient and clinician assessment scores. After Phase 1 is completed the next generation cannula test #1 will be able to start, as deemed appropriate by the clinician.

Baseline Characterization will be performed just prior to the therapy acclimatization segment of this Phase. If there is a reason the clinician does not deem the patient appropriate for the study, per inclusion/exclusion criteria, they may stop procedures during baseline characterization. The inpatient may be sitting or lying down in a comfortable environment. The patient will be set up and prepared for the cannula testing with appropriate data recording devices. While subject is at rest, the following data will be collected (see Table 1): RR, HR, BP, SpO2, TcPCO2 and RPD (Modified Borg scale 0-10). For the RPD, the clinician will record patient scores. The patient may or may not be on HVNI therapy at this time. The Phase 1, baseline characterization will include recording data while the patient is in an uncompromised state (e.g. ON current oxygen therapy, if applicable).

Therapy acclimatization (5 – 10 minutes) will be performed immediately after the baseline characterization segment is complete, and in accordance with site standard of care practices to maintain patient safety. The patient will be fitted with appropriately sized nasal cannula from the conventional legacy design (not to exceed 50% occlusion of the nares). Patients will be notified of best practice for the therapy, and clinicians will record whether patients prefer to keep their mouths open or closed. The acclimatization segment is the interval during which HVNI is to be titrated to provide the patient the appropriate settings for effective HVNI therapy. After the final FiO2/Flow settings are implemented and the patient is acclimatized the following data will be collected (see Table 1): RR, HR, BP, SpO2, TcPCO2 and RPD (Modified Borg scale 0-10). For the RPD, the clinician will record patient scores. Effective flow is recorded.

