## Phase 2 - Test #1 (randomized)

This test session is represented by Phase 2 in Figure 1, where the patient is placed on HVNI therapy with the order-randomized next generation cannula designs. Phase 2 will follow four distinct segments: (1) baseline characterization, (2) therapy acclimatization, (3) therapeutic characterization, (4) patient and clinician assessment scores.

Baseline Characterization will be performed just prior to the therapy acclimatization segment of this Phase. If there is a reason the clinician does not deem the patient appropriate for the study, per inclusion/exclusion criteria, they may stop procedures during baseline characterization. Sitting down in a comfortable environment, the patient will be setup and prepared for the cannula testing with appropriate data recording devices. The patient will be ON current/home oxygen therapy at this time. While subject is at rest, the following data will be collected (see Table 1): RR, HR, BP, SpO2, TcPCO2 and RPD (Modified Borg scale 0-10). For the RPD, the clinician will record patient scores.

Therapy acclimatization (5 – 10 minutes) will be performed after the baseline characterization segment is complete, and in accordance to site SOC to maintain patient safety. The patient will be fitted with appropriately sized nasal cannula (not to exceed 50% occlusion of the nares).

- IF order-randomized to the Unicorn cannula, then use the FiO2 & one-half the Flow settings from Phase 1 as a reference for the Therapeutic Settings.
  - For nostril selection of Unicorn cannula: Ask the patient to state which nostril is easiest to breathe through. Use that nostril to place the Solo/Unicorn cannula.
- IF order-randomized to the Prosoft cannula, then use the FiO2 & the Flow settings from Phase 1 as a reference for the Therapeutic Settings.

After the designated FiO2/Flow settings are implemented and the patient is acclimatized, the following data will be collected (see Table 1): RR, HR, BP, SpO2, TcPCO2 and RPD (Modified Borg scale 0-10). For the RPD, the clinician will record patient scores. Patient perception assessment will also be evaluated at this time.

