NOTE: Should the patient or clinician deem that the therapy is not providing a comparable relief of dyspnea, then after recording the data stated above, proceed to increase titration of the flow until relief of symptoms, with attention to TcPCO2. At this time, the therapy acclimatization segment should be repeated, and data will be appropriately recorded to account for this 'settings' adjustment. This is to understand any difference in cannula efficacy between legacy design and next generation cannula, designs.

Therapeutic Characterization will be performed 5-10 minutes after the therapy acclimatization segment is completed. This will provide the patient sufficient time to receive clinical effect of the HVNI therapy and become sufficiently comfortable with the therapy and cannula. Once the respiratory therapist or other clinician skilled in management of HVNI deems that the HVNI settings are having a therapeutic effect, the following data will be collected (see Table 1): RR, HR, BP, SpO2, TcPCO2 and RPD (Modified Borg scale 0-10). For the RPD, the clinician will record patient scores.

Patient & Clinician Perception Assessment will be performed by the clinician or therapist performing this phase's testing procedures. Immediately following the completion of this phase, as soon as possible, the continuous Visual Acuity Scale (VAS) will be completed for each of the five endpoints for clinician assessment and the two endpoints for the patient assessment. For the patient perception these include: (1) relief of symptoms, and (2) comfort/tolerance. For the clinician perception these include: (1) technical/clinical difficulties, (2) patient comfort & tolerance, (3) ease of use, (4) monitoring & support for therapy, and (5) expected/perceived patient outcomes.

**Upon completion of this phase**, the testing will pause for 15 minutes, until patient has returned to baseline dyspnea, prior to continuing with the next nasal cannula design test. During this pause the patient will not perform known to worsen dyspnea. During the pause the patient will continue with their current oxygen therapy.

Phase 3 - Test #2 (randomized)

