## VII. Data Collection

## Table 1. Key study data and collection points for each Phase of the Study.

	Baseline Characterization	Therapy Acclimatization	Therapeutic Characterization	@ Study End
Patient History & Health	Х			
Treatment: Flow & O2	Х	Х	Х	
Physiologic Parameters	Х	Х	Х	
Ventilation Parameters	Х	Х	Х	
Clinician Perception Scores			X	Х
Patient Perception Scores			Х	Х

Patient enrollment data collection will include patient history, health, demographics, and current respiratory therapies. Only Phase 1 will record the patients' history and background information. For each segment of each phase, the following data will be recorded for comparison:

Physiologic Parameters o SpO2, HR, RR, BP Ventilation Parameters o RPD, TcPCO2

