## Secondary Endpoints

- Physiologic parameter(s) SpO2, HR, RR, BP
- Ventilation parameter(s) –TcPCO2

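### Goal 2 claims comparable relief with Unicorn at lower flows, but flow may be raised before the final dyspnea reading and no endpoint or specified analysis shows whether it stayed lower

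*Combined protocol and SAP*

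**What the plan says.** - **Goal.** Section I sets a second goal for Unicorn: to "assess if next generation Solo (Unicorn) cannulas at lower flows provide comparable dyspneic relief". The comparator in that sentence is unclear. Section II names the legacy cannula, and I take that.
- **Hypothesis.** Section II expects both new designs to be comparable to legacy for dyspnea relief. The lower-flow condition does not appear there.
- **Starting setting.** Under Phase 2, staff are to "use the FiO2 & one-half the Flow settings from Phase 1" for Unicorn, as a reference point. Dyspnea and the other measures are recorded once the patient is acclimatized at that setting.
- **Change of setting.** If patient or clinician judges relief not comparable, staff first record those data and then "proceed to increase titration of the flow until relief of symptoms, with attention to TcPCO2". The acclimatization segment is repeated and "data will be appropriately recorded to account for this 'settings' adjustment". The stated purpose is: "This is to understand any difference in cannula efficacy between legacy design and next generation cannula, designs". Phase 3 repeats these procedures.
- **Outcome time.** Section IV takes the final data for each cannula at therapeutic characterization and completes primary and secondary outcomes at the end of each phase.
- **Flow data.** Table 1 has a row "Treatment: Flow & O2", marked for baseline, acclimatization and therapeutic characterization. For Phase 1 the text adds "Effective flow is recorded".
- **Endpoints and analysis.** The primary endpoint is Borg rated perceived dyspnea (RPD). The secondary endpoints are SpO2, HR, RR, BP and TcPCO2; the tertiary ones are perception scores. Flow is in none of these, nor among the variables Section VII lists for comparison. Section VIII applies a signed-rank test (or t-test) to all applicable variables without naming flow.

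**The concern.** Goal 2 is conditional: it concerns relief while flow is lower than with legacy. The procedure raises flow precisely in patients whose relief falls short, so it pulls the final RPD towards comparability. If the final RPD is the outcome, as Section IV suggests, a comparable result no longer shows that the condition held. Delivered flow is the variable that would reveal this. It is collected, but the plan gives it no role in judging the goal. At stake is the claim that sets Unicorn apart: it could be reported as supported when the data show only that Unicorn relieves dyspnea once flow has been raised.

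**Working it through.** **1. The plan's own figure.** Section V (Sample Size) gives difference 2, SD 3, power 90%, alpha 0.05, paired t-test, N = 26.

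- Normal approximation, two-sided: n = (3 × (1.960 + 1.282) / 2)² = 23.6, so 24.
- Noncentral t, two-sided: n = 26, power 90.4%.

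The stated 26 reproduces if the test is two-sided (sidedness is not stated). It covers RPD only. No flow SD, target reduction or required share of patients is given, so no sample size for flow can be derived.

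**2. One patient followed through the plan.** Take a legacy flow of 30 L/min, an illustrative value inside the 20 to 35 L/min target under Phase 1. Unicorn starts at 30 / 2 = 15 L/min. Suppose relief is judged not comparable and flow is raised to 30 L/min. Nothing in the note rules this out. The final flow ratio is 30 / 30 = 1. If the final RPD equals the legacy RPD, the patient counts towards comparability, and no listed endpoint shows that flow was not lower.

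**3. Effect on the RPD comparison (illustration).** Assumptions: 26 completers; paired SD 3; a true deficit D at half flow; a share s of patients, chosen at random, has flow raised; raising flow removes the whole deficit. The final paired difference then has

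- mean = D(1 − s)
- SD = √(9 + D² s(1 − s))

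For D = 2 and s = 0.5, the mean is 1, the SD is √10 = 3.16, and the noncentrality is √26 × 1 / 3.16 = 1.61. Chance of a two-sided p < 0.05, from 20,000 simulated trials per case:

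| True deficit at half flow | Half-flow RPD | Final RPD, half raised | Final RPD, all raised |
|---|---|---|---|
| 2 points | about 90% | about 34% | about 5% |
| 1 point | about 38% | about 13% | about 5% |

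The 5% is simply the type I error rate: once all patients are raised, no deficit is left to find. The table shows what depends on the choice of reading. It does not estimate how often flow would be raised.

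**4. Precision available for flow.** Exact (Clopper-Pearson) 95% intervals for the proportion still below their own Phase 1 flow, using assumed counts out of 26:

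- 26: 86.8% to 100%
- 23: 69.8% to 97.6%
- 20: 56.4% to 91.0%
- 13: 29.9% to 70.1%

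**The case against.** The strongest reply is that lower flow is a condition set by design, not an outcome. Unicorn starts at half flow and RPD is recorded there before any increase. If that reading decides goal 2, the condition holds by construction and no flow endpoint is needed. This stands as far as it goes: the data to test goal 2 will exist. A reader might infer that the goal is untestable whichever RPD reading is used, and the documents do not support that. But the plan does not choose the half-flow reading, and Section IV points to the end of the phase.

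Three other stronger readings also fail.

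- **That flow will never be analysed.** Section VIII's reference to all applicable variables could loosely include it. The accurate statement is that no analysis is specified.
- **That increases are likely, because half of 20 to 35 (up to 40) L/min is 10 to 17.5 (up to 20) L/min, below the 25 to 40 L/min in Section I.** That range concerns purging the upper airway through the sponsor's adult cannulae. It is not a threshold for dyspnea relief and is not stated for a single-prong design. The legacy target itself begins at 20 L/min. Section IV expects titration after Phase 1 only on decompensation; the Phase 2 note has a broader trigger, and the two passages should be reconciled.
- **That 26 patients would cleanly separate success from failure on flow.** The counts in the working are assumed, neighbouring intervals overlap, and the documents set no threshold.

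It is also fair to object that flow is changed on unblinded judgement. That limits how far flow can stand as an efficacy measure, but not its use in checking whether the goal's condition was met.

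**Conclusion.** The concern holds in this form: followed as written, the plan could report goal 2 as met on a final RPD taken at flows no lower than legacy, because flow may be raised without a stated cap relative to Phase 1 and has no endpoint or specified analysis. The size depends on the share of patients raised, which the documents do not give. In the illustration, detection of a true 2-point deficit runs from about 90% (none raised) through 34% (half) to 5% (all), assuming SD 3, 26 completers and full correction. The primary RPD analysis still runs and the necessary data are collected, so this should be corrected but does not undermine the whole trial. The goal says lower flows, not half the legacy flow: a patient relieved at 70% of legacy flow would still meet it. Goal 1 makes no lower-flow claim for Prosoft.

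**What to change.** All of this uses data already recorded and changes no titration rule or flow setting.

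1. **Endpoint.** For Unicorn, add as a secondary endpoint the within-patient difference or ratio of flow at therapeutic characterization versus Phase 1 legacy flow, with a 95% CI. Report with it the number and proportion of patients whose flow was raised, and the proportion still below their own Phase 1 flow, with exact CIs. The proportion is needed because an average ratio below 1 can hide patients at or above legacy flow.
2. **Hypothesis.** Restore the lower-flow condition to the Unicorn part of the hypothesis in Section II, worded as lower flows and not as half the legacy flow.
3. **Decision rule.** Base the goal 2 conclusion on the RPD recorded at the designated half-flow setting before any increase, set against the legacy reading from the same segment. Alternatively, if the final RPD is used, claim relief at lower flows only when the CI for the within-patient flow ratio versus legacy lies below 1.
4. **Prosoft.** A descriptive summary of flow is enough.

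The cost is an amendment to the objectives, endpoint list and Section VIII, made before the data are examined. The downside for the sponsor is a narrower Unicorn claim if many patients need the flow raised. The half-flow reading also reflects a shorter exposure than the final one.
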